9.5.1.2 Abdominal Aortic Aneurysm (AAA)

Summary of the maximum minor-axis AAA Diameter	
Population	: FAS
Group	
• Study Arm• Product Use Category
Contents	: Descriptive statistics for the maximum minor-axis AAA diameter and change from baseline at each visit will be presented.
Target visit	: V1, V3 to V8
Output	Summary of the maximum minor-axis AAA Diameter -FAS-

Confidentiality Statement

Data and information contained in this document are considered to constitute trade secrets and confidential commercial information, and the legal protections provided to such trade secrets and confidential information are hereby claimed under the provisions of applicable law. No part of this document may be publicly disclosed without the written consent of Philip Morris Products S.A.

Summary of the maximum minor-axis AAA Diameter	
	Summary of the maximum minor-axis AAA Diameter by Product Use Category -FAS-
	Figure of the maximum minor-axis AAA Diameter -FAS-
	Figure of the maximum minor-axis AAA Diameter by Product Use Category -FAS-
	Listing of Maximum minor-axis AAA Diameter Growth

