Confidentiality Statement

Data and information contained in this document are considered to constitute trade secrets and confidential commercial information, and the legal protections provided to such trade secrets and confidential information are hereby claimed under the applicable provisions of applicable law. No part of this document may be publicly disclosed without the written consent of Philip Morris Products S.A.

Besides its role as the most important risk factor for developing AAA, smoking also significantly accelerates the growth of an AAA. The growth rate observed in CC smokers is higher than it is in former CC smokers (an increase of approximately 0.4 mm/year)^{12,13}. Through the impact on growth rate, CC smoking also increases the risk of an AAA rupture and decreases the time to AAA open surgical/endovascular repair intervention^{13,14}. Furthermore, a larger aneurysm size at diagnosis indicates a more rapid expansion of the aneurysm further on and therefore a faster disease progression¹⁰. Abdominal Aortic Aneurysms that reach a diameter of ≥ 55 mm in males or ≥ 50 mm in females, as well as AAA that have a growth rate of ≥ 5 mm within 6 months are common indicators for open surgical interventional treatment or AAA endovascular repair of the AAA¹.

Philip Morris International (PMI) develops, assesses and commercializes a portfolio of innovative products intended to (1) significantly reduce the risk of smoking-related disease compared to continued smoking of CC and (2) are accepted by smokers as substitutes for CC.

More than 6000 smoke constituents have been identified when the tobacco is burned or combusted¹⁵, and more than 100 of them have been categorized as harmful and potentially harmful constituents (PHHCs)¹⁶. Lowering the temperature and heating the tobacco instead of burning it can substantially reduce levels of PHHCs. PMI's Tobacco Heating System (THS, marketed under the brand name of IQOS) is a novel tobacco heating system that heats a specifically designed tobacco stick (*HeatStick*) within a precisely controlled temperature range (far lower temperatures than CC) rather than burning it. IQOS replicates the ritual of smoking but without combustion.^{15,16}.

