5.2 Discontinuation of Patients from the Study

Discontinued patients will include patients who withdraw from the study (patient's decision) and patients who are discontinued from the study by the decision of the Investigator. A patient can only be discontinued from the study after enrollment.

Patients will be informed that they are free to withdraw from the study at any time. Patients should be asked for the reason of withdrawal from the study, although they are not obliged to disclose it.

Confidentiality Statement

Data and information contained in this document are considered to constitute trade secrets and confidential commercial information, and the legal protections provided to such trade secrets and confidential information are hereby claimed under the applicable provisions of applicable law. No part of this document may be publicly disclosed without the written consent of Philip Morris Products S.A.

If the patient withdraws from the study, he/she will be asked to perform the early termination procedures (section 9.4) as soon as possible after the time of withdrawal unless the patient refuses to do it in writing.

The patient will be reminded that the data collected until the point of withdrawal will be maintained as part of the study data, and the samples collected prior to withdrawal or during the early termination visit will be analyzed after his withdrawal, unless he/she refuses in writing.

All discontinued patients cannot re-enter the study.

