5.2.1 Discontinuation from the study

Patients must be discontinued from the study for any of the following reasons:

- Withdrawal of informed consent.
- Discontinuation is considered to be in the interest of the patient from a safety perspective as judged by the Investigator.
- Positive or unclear pregnancy test.
- The Sponsor or Investigator terminates the study or the study terminates at a particular investigational site. If the Sponsor or the Investigator decides to prematurely terminate the study, the patient will be promptly informed. The investigational site/head of the medical institution should report the fact and the reason in writing to the IRB / IEC.
- Patient has to undergo open surgical AAA treatment or AAA endovascular repair (as per the treating physician's decision based on the standard of care as documented in the Guidelines for Diagnosis and Treatment of Aortic Aneurysm and Aortic Dissection¹).
- The patient experiences a rupture of his/her AAA.
- Patient becomes an employee of the investigational site, a tobacco company or any other parties involved in the study.
- Lost to follow-up.

Patients may be discontinued from the study for the following reasons:

- Non-compliance to the study procedures based on the judgment of the Investigator.

If a violation of selection criteria is detected after enrollment, patients might be discontinued from the study based on a case-by-case decision of the Investigator.

Confidentiality Statement

Data and information contained in this document are considered to constitute trade secrets and confidential commercial information, and the legal protections provided to such trade secrets and confidential information are hereby claimed under the applicable provisions of applicable law. No part of this document may be publicly disclosed without the written consent of Philip Morris Products S.A.

Patients will not be discontinued from the study for the use of tobacco or nicotine-containing products other than their assigned product/regimen unless judged by Investigator.

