3 STUDY OBJECTIVES AND ENDPOINTS

3.1 Primary Objectives and Endpoints

The primary objective of this study is:

To evaluate the reduction in the AAA annual growth rate in patients who switch from smoking cigarettes (CIG) to using IQOS, as compared to patients who continue to smoke CIG (IQOS arm versus cigarette arm), also as compared to patients who had stopped smoking (IQOS arm

Confidentiality Statement

Data and information contained in this document are considered to constitute trade secrets and confidential commercial information, and the legal protections provided to such trade secrets and confidential information are hereby claimed under the provisions of applicable law. No part of this document may be publicly disclosed without the written consent of Philip Morris Products S.A

versus Smoking Cessation (SC) arm), and to evaluate the reduction in the AAA annual growth rate in patients who continue to smoke CIG as compared to patients who had stopped smoking (CIG arm versus SC arm).

Endpoints (to be assessed using all available diameter measurements from V3 to V8):

- Measurement of the maximum minor-axis AAA diameter in mm
- AAA annual growth rate (calculated by annualizing the slope of the linear regression over the available diameter measurements)

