9.1.3 Descriptive Statistics

Data will be presented in listings, enrollment arm, patient, and study visit, unless otherwise specified.

For continuous data, summary statistics will include the number of patients with non-missing values [n], number and percent of patients with missing data, the mean and standard deviation (SD), median, first and third quartiles, minimum and maximum, and 95% confidence interval (CI). Log-normally distributed data (e.g., BoExp data) will also include the geometric mean and coefficient of variation (CV) in addition to the mean and SD. Post-baseline summaries will include change from baseline apart from log-normal variables which will present % change from baseline (see Section 5.1.2).

Confidentiality Statement

Data and information contained in this document are considered to constitute trade secrets and confidential commercial information, and the legal protections provided to such trade secrets and confidential information are hereby claimed under the provisions of applicable law. No part of this document may be publicly disclosed without the written consent of Philip Morris Products S.A.

For categorical data, frequency counts and percentages will be presented. Percentages of missing values will be computed using the number of patients [N] included in the corresponding group in the denominator, while percentages related to ‘non-missing’ categories will be computed using the number of patients with non-missing values in the denominator.

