9.1.5 Handling of Dropouts or Missing Data

For BoExp parameters:

- Values below the lower limit of quantification (LLOQ) will be imputed using LLOQ/2. For values above the upper limit of quantification (ULOQ), the ULOQ will be imputed.
- The number and percentage of values below LLOQ or above ULOQ will be presented in each summary table (the percentage of values below LLOQ/ULOQ will use the number of patients with non-missing values in the denominator). If more than 50% of the data are below LLOQ, only the number and percentage of values below LLOQ will be reported in the summary together with the minimum and maximum values.

For self-reported tobacco or nicotine-containing product use:

- Only available data will be included in the product use summaries.

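### By-visit AAA diameter means (SAP 9.5.1.2) omit patients already repaired or ruptured, so late means run too low in each arm; the effect on the arm difference depends on how repair is decided

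*SAP*

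**What the plan says.** SAP 3.1 lists two endpoints under the primary objective. The first is "Measurement of the maximum minor-axis AAA diameter in mm"; the second is the annual growth rate. For the first, SAP 9.5.1.2 plans: "Descriptive statistics for the maximum minor-axis AAA diameter and change from baseline at each visit will be presented". The table and figure cover V1 and V3 to V8, in the FAS, by study arm and by product use category. SAP 9.1.3 defines the summary through "the number of patients with non-missing values [n], number and percent of patients with missing data", so each mean is taken over patients measured at that visit and the others are only counted.

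Protocol 5.2.1 lists events after which a patient must be discontinued. Two of them are "Patient has to undergo open surgical AAA treatment or AAA endovascular repair" and "The patient experiences a rupture of his/her AAA". Protocol 5.2 adds: "All discontinued patients cannot re-enter the study". Protocol 2.1 says that diameters of at least 55 mm in men or 50 mm in women, or growth of at least 5 mm within 6 months, "are common indicators for open surgical interventional treatment or AAA endovascular repair of the AAA".

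No rule recovers a diameter lost this way. SAP 9.1.5 deals with biomarker quantification limits and with product use, for which it says "Only available data will be included in the product use summaries"; diameter is not mentioned. Protocol Table 7 lists no CT scan at early termination. SAP 9.1.6 keeps unscheduled data out of the tables. Protocol 7.4.9 has the centrally read diameter at the repair decision recorded in the CRF, but SAP 9.5.1.2 does not use it.

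**The concern.** Whether a diameter is missing depends on the diameter itself. A patient whose aneurysm becomes large or grows fast is repaired, leaves the study, and contributes nothing to later visits. The V7 and V8 means then describe patients who have not yet needed repair, under a label that says FAS. The plotted curve bends downward for a reason unrelated to slower growth.

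If one arm grows faster and every arm is managed by the same repair rule, that arm loses more of its largest aneurysms and the gap between the late means narrows. The 95% intervals beside those means reflect sampling error only, so they give no sign of this.

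**Working it through.** **Nothing to reproduce.** The documents give no sample size calculation, mean growth rate, SD of growth or repair rate. The size can only be shown as a range under assumptions. (The SAP writes CIG for the arm that the protocol calls CC.)

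**Inputs from the documents**
- Entry diameter 30 to 49 mm in men, 30 to 44 mm in women (Protocol 5.1.1)
- Scans at V1 and every 6 months from V3 to V8, at 36 months (Protocol 9.3, Appendix 1)
- Size indications for repair 55 mm in men, 50 mm in women (Protocol 2.1)
- Growth difference 0.4 mm/year, smokers versus former smokers (Protocol 2.1)
- 32 of 114 planned patients enrolled when the decision to stop recruitment was explained (Protocol 4.4)

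**Who can be lost by V8.** The scheduled scan that triggers repair stays in the table, so the loss starts at the next visit. To be absent at V8 for size, a man must reach 55 mm by V7, 2.5 years after V2:
- from 49 mm: (55 − 49)/2.5 = 2.4 mm/year
- from 45 mm: (55 − 45)/2.5 = 4.0 mm/year
- from 40 mm: (55 − 40)/2.5 = 6.0 mm/year

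The margin is the same for a woman entering at 44 mm (50 − 44 = 6 mm). The loss is therefore concentrated in patients who enter near the upper limit, and at late visits.

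**True V8 difference.** 3 years × 0.4 mm/year = 1.2 mm.

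**Simulation with size-based exit.** Assumptions: baseline uniform on 30 to 49 or 35 to 49 mm; between-patient SD of growth 1 to 2 mm/year; reading SD 1 mm; exit after the visit at which the site reads 55 mm or more, with the same rule in both arms.

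| Growth, IQOS v CIG (mm/year) | V8 difference in mean diameter (true 1.2 mm) |
|---|---|
| 2.5 v 2.9 | 0.77 to 0.88 mm |
| 1.5 v 1.9 | 0.90 to 1.04 mm |

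- At 2.5 v 2.9 with baseline 35 to 49 mm, 9 to 16% (IQOS) and 13 to 20% (CIG) are missing at V8, and the V8 means are too low by 0.8 to 2.0 mm and 1.2 to 2.4 mm. Over all settings the V8 bias runs from about 0.2 to 2.4 mm.
- In the faster-growth setting the V6 means are off by only about 0.1 to 0.5 mm.
- The V8 difference in change from baseline is 0.94 to 1.15 mm.

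**Second simulation, wider assumptions.** Baseline Normal(41, 5) truncated to 30 to 49 mm; CIG growth 2, 3 or 4 mm/year; SD of growth 1 or 2 mm/year; reading SD 0.5 or 1.0 mm; exit also for growth of 5 mm or more in 6 months.
- With a 55 mm threshold the V8 difference is 0.66 to 1.07 mm. It shrank in all 24 scenarios, which also included a 50 mm threshold.
- With no true difference, none arises (about 0.01 to 0.02 mm).
- The mean difference in per-patient slopes is 0.39 to 0.45 mm/year against a true 0.40.
- Unequal repair decisions (CIG growth 3 mm/year, SD 2, threshold 55 mm): if CIG patients are always repaired once eligible and IQOS patients with 30% probability per visit, the V8 difference is −0.30 mm; with the reverse it is 2.06 mm.

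**Precision.** At an assumed 11 patients per arm and SD 5 mm, the 95% half-width for a difference in means is 1.96 × 5 × √(2/11) = 4.2 mm.

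**Does a mixed model help at this size?** At 11 per arm, a model with visit as a factor and a random intercept and slope converged in all 200 simulated trials. It reduced V8 bias from −1.4 and −1.7 mm in the two arms to under 0.1 mm. Against the difference the same patients would have shown with no exits, root mean squared error fell from 1.65 to 0.29 mm.

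**The case against.** The strongest reply has four parts.

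1. The study is descriptive, and the comparison that Protocol 12.6 and SAP 9.5.1.1 call the primary endpoint is the growth slope, which uses the scans before exit. This stands: the slope is largely spared, and the point concerns the other listed endpoint only.
2. The table also gives change from baseline, which keeps most of the difference. This stands too. The late raw means and the figure remain affected.
3. Exits are visible elsewhere: the table counts missing patients, and SAP 9.5.2 reports repair and rupture as Kaplan-Meier curves and incidence rates, plus counts above the size and growth limits. A reader might infer that the plan would hide harm from IQOS; the documents do not support that. But those outputs neither correct the diameter means nor say which missing values follow repair or rupture.
4. With about 32 patients over three arms, the attenuation (1.2 − 1.04 = 0.16 to 1.2 − 0.77 = 0.43 mm) is small beside a half-width of about 4.2 mm. True, but the interval does not allow for the bias, and in an arm of 11 one or two exits move the mean.

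A reader might also infer that the difference between arms must shrink. That holds only if the arms truly differ and the same repair rule is applied in all of them. Protocol 7.4.9 leaves the decision to the site's own CT assessment in an open-label study, so it is not assured.

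**Conclusion.** The point holds. Followed as written, SAP 9.5.1.2 yields late by-visit diameter means that leave out patients already repaired or ruptured and are too low in each arm, by about 0.2 to 2.4 mm at V8 under the first simulation's assumptions. With a true difference of 0.4 mm/year and a common repair rule, 1.2 mm at V8 appears as about 0.8 to 1.0 mm in mean diameter and about 0.9 to 1.15 mm in change from baseline. With unequal repair decisions the distortion can go either way.

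These sizes rest on assumed growth rates and SDs. The 0.4 mm/year is a smoker versus former-smoker figure, so using it for IQOS versus CIG assumes a cessation-like benefit. With slow growth or few patients near the entry limit, exits would be few and the bias small.

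**What to change.** In SAP 9.5.1.2:
- Keep the observed-case table.
- Add by-visit LS means with 95% CI, and base the figure on them, from a mixed model of all scheduled centrally read diameters (V1, V3 to V8) with arm, visit, arm × visit and a random intercept and slope per patient. Use a random intercept only if the model fails to converge.
- Under the observed-case table print, by arm and visit, the number absent because of repair or rupture and their last diameter.

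The cost is a paragraph of SAP text and one further PROC MIXED run on data already collected; SAP 9.5.2.2 already specifies a repeated-measures mixed model for the exposure biomarkers. The downside should be stated with the results: the model assumes that exit depends on the observed diameters, and its late means describe the diameter expected had repair not occurred.

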9.5.2 Secondary Analyses

9.5.2.1.1 Time to Event

Time from Diagnosis of the AAA until Open Surgical AAA Treatment or AAA Endovascular Repair		
Population	:	FAS
Group	:	
• Study Arm• Product Use Category
Contents		
• Create a Kaplan Meier curve for the following events
➢ Open surgical or endovascular repair of AAA➢ Rupture of AAA• Calculate the number of subjects at risk for each of the group.
Definitions		
• Calculate the time to the event by the following equation.
➢ Open surgical or endovascular repair Date of decision to perform surgery – date of diagnosis + 1 = time to the event➢ Rupture of AAA Date of AAA rupture – date of diagnosis + 1 = time to the event• Censor: if a subject does not experience the event, then treat the subject event as censor. Use the last subject visit date.

Confidentiality Statement

Data and information contained in this document are considered to constitute trade secrets and confidential commercial information, and the legal protections provided to such trade secrets and confidential information are hereby claimed under the provisions of applicable law. No part of this document may be publicly disclosed without the written consent of Philip Morris Products S.A.

Time from Diagnosis of the AAA until Open Surgical AAA Treatment or AAA Endovascular Repair	
Remarks	: The date of actual performance of surgery is not determined from the CRF. Instead, the date of decision to perform the surgery will be used for open surgical or endovascular repair of AAA.
Program	Time (months) = (Date of Event – date of diagnosis + 1) / 30.4375 proc lifetest data=BMT plots=survival (atrisk=0 to 18 by 6); time time*status(0); strata group; run; Output Kaplan-Meier estimates at each fixed time point (6, 12, 18, 24, 30, 36 months) along with their 95% CIs. 95% confidence limits are calculated by log-log transformation using standard error (SE) derived by Greenwood's Formula. Also, 25 th percentile, median, and 75 th percentile of Survival time with their respective 95% confidence intervals
Output	Time from Diagnosis of the AAA until Open Surgical AAA Treatment or AAA Endovascular Repair -FAS- Time from Diagnosis of the AAA until Open Surgical AAA Treatment or AAA Endovascular Repair by Product Use Category -FAS- Summary of Time from Diagnosis of the AAA until Open Surgical AAA Treatment or AAA Endovascular Repair -FAS- Summary of Time from Diagnosis of the AAA until Open Surgical AAA Treatment or AAA Endovascular Repair by Product Use Category -FAS- Time from diagnosis of the AAA until time to rupture AAA -FAS- Time from diagnosis of the AAA until time to rupture AAA by Product Use Category -FAS- Summary of Time from diagnosis of the AAA until time to rupture AAA -FAS- Summary of Time from diagnosis of the AAA until time to rupture AAA by Product Use Category -FAS- Listing of Statistical Output (LIFETEST procedure)

Confidentiality Statement

Data and information contained in this document are considered to constitute trade secrets and confidential commercial information, and the legal protections provided to such trade secrets and confidential information are hereby claimed under the provisions of applicable law. No part of this document may be publicly disclosed without the written consent of Philip Morris Products S.A

Time from Diagnosis of the AAA until Open Surgical AAA Treatment or AAA Endovascular Repair

Listing of Statistical Output (LIFETEST procedure) by Product Use Category

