3.2 Secondary Objectives and Endpoints

The secondary objectives of this study are:

1. To describe the time from diagnosis of the AAA until open surgical AAA treatment or AAA endovascular repair or AAA rupture in patients who switch from smoking CC to using IQOS, as compared to patients who continue smoking CC and patients who had stopped smoking.

Endpoints (over the entire study period):

- Date of diagnosis
- Date of decision to perform open surgical AAA treatment or AAA endovascular repair
- Date of AAA rupture

2. To describe the number of open surgical AAA treatment or AAA endovascular repair and AAA rupture in patients who switch from smoking CC to using IQOS, as compared to patients who continue to smoke CC and patients who had stopped smoking.

Endpoints (number per year across all visits):

Confidentiality Statement

Data and information contained in this document are considered to constitute trade secrets and confidential commercial information, and the legal protections provided to such trade secrets and confidential information are hereby claimed under the applicable provisions of applicable law. No part of this document may be publicly disclosed without the written consent of Philip Morris Products S.A.

- Number of patients with open surgical AAA treatment or AAA endovascular repair annually (based on date of decision to perform open surgical AAA treatment or AAA endovascular repair)
- Number of patients with AAA rupture annually (based on date of AAA rupture)

3. To evaluate the number of AAA growth above 5 mm in 6 months and the number of patients with an overall maximum minor-axis AAA diameter >55mm in male patients and >50mm in female patients, in patients who switch from smoking CC to using IQOS, as compared to patients who continue smoking CC and patients who had stopped smoking.

Endpoints (number per year across all visits):

- Number of patients with an increase in maximum minor-axis AAA diameter of more than 5 mm within 6 months
- Number of patients with an overall maximum minor-axis AAA diameter >55mm in male patients and >50mm in female patients

4. To monitor the safety profiles associated with IQOS use, CC smoking, and SC during the study.

Endpoints (over the entire study period):

- Incidence of adverse events (AEs) / serious adverse events (SAEs)
- Vital signs - change from Baseline (systolic and diastolic blood pressure, pulse rate and respiratory rate)

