12.7 Secondary Analysis

Descriptive statistics for the maximum minor-axis AAA diameter will be summarized at each visit and overall (across all patients). The endpoints will also be summarized by strata (maximum-minor-axis AAA diameter, CC consumption, sex).

Urinary NEQ, and Total NNAL, Total NNN, and CEMA levels (concentration data adjusted for creatinine will be analyzed on a logarithmic scale) using an MMRM with the logarithmic transformation.

Descriptive statistics for the secondary endpoints shown below, will be summarized at each visit, except for vital signs (systolic and diastolic blood pressure) which will be summarized

Confidentiality Statement

Data and information contained in this document are considered to constitute trade secrets and confidential commercial information, and the legal protections provided to such trade secrets and confidential information are hereby claimed under the applicable provisions of applicable law. No part of this document may be publicly disclosed without the written consent of Philip Morris Products S.A.

every 12 months, by exposure group and overall (across all patients) in the FAS (unless otherwise defined):

- Time from diagnosis of AAA until open surgical AAA treatment or endovascular repair
- Time from diagnosis of AAA until AAA rupture
- Annual growth rate of AAA
- Nicotine equivalents (NEQ): molar sum of free nicotine, nicotine-glucuronide, free cotinine, cotinine-glucuronide, free trans-3'-hydroxycotinine, trans-3'-hydroxycotinine-glucuronide in spot urine (expressed as concentration adjusted to creatinine)
- Systolic and diastolic BP
- Body weight and waist circumference

For the secondary endpoints shown below, the number at each visit and overall (across all patients) will be described:

- Number of patients with open surgical AAA treatment or endovascular repair annually (based on date of decision to perform open surgical AAA treatment or AAA endovascular repair)
- Number of patients with a AAA rupture annually (based on date of AAA rupture)
- Number of patients with an increase in maximum minor-axis AAA diameter of more than 5 mm within 6 months
- Number of patients with an overall maximum minor-axis AAA diameter >55mm in male patients and >50mm in female patients
-
- Incidence of IQOS malfunctions and misuses
- Number of tobacco products used, (including CC and HeatSticks) based on self-reporting

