3.2 Secondary Objectives and Endpoints

The secondary objectives of this study are:

1. To describe the time from diagnosis of the AAA until open surgical AAA treatment or AAA endovascular repair or AAA rupture in patients who switch from smoking CIG to using IQOS, as compared to patients who continue smoking CIG and patients who had stopped smoking.

Endpoints (over the entire study period):

- Date of diagnosis
 - Date of decision to perform open surgical AAA treatment or AAA endovascular repair
 - Date of AAA rupture
2. To describe the number of open surgical AAA treatment or AAA endovascular repair and AAA rupture in patients who switch from smoking CIG to using IQOS, as compared to patients who continue to smoke CIG and patients who had stopped smoking.

Endpoints (number per year across all visits):

- Number of patients with open surgical AAA treatment or AAA endovascular repair annually (based on date of decision to perform open surgical AAA treatment or AAA endovascular repair)
 - Number of patients with AAA rupture annually (based on date of AAA rupture)
3. To evaluate the number of AAA growth above 5 mm in 6 months and the number of patients with an overall maximum minor-axis AAA diameter >55mm in male patients and >50mm in female patients, in patients who switch from smoking CIG to using IQOS, as compared to patients who continue smoking CIG and patients who had stopped smoking.

Endpoints (number per year across all visits):

- Number of patients with an increase in maximum minor-axis AAA diameter of more than 5 mm within 6 months
- Number of patients with an overall maximum minor-axis AAA diameter >55mm in male patients and >50mm in female patients

Confidentiality Statement

Data and information contained in this document are considered to constitute trade secrets and confidential commercial information, and the legal protections provided to such trade secrets and confidential information are hereby claimed under the provisions of applicable law. No part of this document may be publicly disclosed without the written consent of Philip Morris Products S.A

4. To monitor the safety profiles associated with IQOS use, CIG smoking and smoking cessation during the study.

Endpoints (over the entire study period):

- Incidence of Adverse events (AEs) / serious adverse events (SAEs)
- Vital signs - change from Baseline (systolic and diastolic blood pressure, pulse rate and respiratory rate)

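### Objective 1 is worded as time to repair or rupture, but the plan analyses the two only separately, each treating the other as ordinary censoring, and produces no time to the first of them

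*SAP*

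**What the plan says.** Secondary objective 1 is the same in Protocol 3.2 and SAP 3.2: "To describe the time from diagnosis of the AAA until open surgical AAA treatment or AAA endovascular repair or AAA rupture", compared across the three groups. The endpoints beneath it are three dates: diagnosis, the repair decision ("Date of decision to perform open surgical AAA treatment or AAA endovascular repair") and rupture. No derived time is defined there.

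Protocol 12.7 lists two times: "Time from diagnosis of AAA until open surgical AAA treatment or endovascular repair" and "Time from diagnosis of AAA until AAA rupture".

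SAP 9.5.2.1.1 carries out those two items. It says "Create a Kaplan Meier curve for the following events" and names repair and rupture. The censoring rule is "if a subject does not experience the event, then treat the subject event as censor", using the date of the last visit. The sample code has one censoring value and no status for a competing event. The outputs are a repair set and a rupture set ("Time from diagnosis of the AAA until time to rupture AAA -FAS" is one of the latter), by arm and by product use category. None combines the two events.

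Protocol 5.2.1 requires discontinuation when a patient has to undergo repair, and also when this occurs: "The patient experiences a rupture of his/her AAA". SAP section 7, on changes from the protocol, does not mention the point.

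**The concern.** The wording of objective 1 most naturally means the time to whichever of repair or rupture happens first. Objective 2 points the same way: it joins repair and rupture with *and* where it counts them as separate items. On that reading, an objective carried in both documents has no matching output.

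The separate curves raise a second issue. A repaired patient leaves the study and is censored in the rupture curve. A patient who ruptures with no recorded repair decision is censored in the repair curve. Kaplan-Meier then treats that patient as if the other event could still be observed later. The censoring is also unlikely to be uninformative: Protocol 2.1 names large diameter and fast growth as common indicators for repair, and Protocol 4.1 says size and growth rate affect the incidence of repair or rupture. One minus Kaplan-Meier is therefore not the proportion of patients who rupture, and it estimates a no-repair risk only under an assumption that the protocol's own background makes doubtful. The gap depends on the repair rate, so it can differ between arms.

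**Working it through.** The plan gives no event rate, event count or power figure for these endpoints, so there is no figure of its own to reproduce.

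**1. Direction on a common time axis.** At each event time both estimators use the same cause-specific hazard. Kaplan-Meier multiplies it by the probability of being free of that event. Aalen-Johansen multiplies it by the probability of being free of both events, which cannot be larger. So one minus Kaplan-Meier is at or above cumulative incidence, with equality for rupture if no rupture follows a repair.

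**2. Size, under assumed rates.** Assume constant, independent hazards: repair r from 0.02 to 0.30 per year, rupture p from 0.002 to 0.02 per year. None of these is in the documents. Follow-up is t = 3 years from entry (Protocol 4.3).

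- Rupture, one minus Kaplan-Meier: 1 − exp(−pt)
- Rupture, cumulative incidence: p/(p+r) × [1 − exp(−(p+r)t)]
- Repair or rupture, first event: 1 − exp(−(p+r)t)

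For r = 0.10 and p = 0.01:

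- One minus Kaplan-Meier = 1 − exp(−0.03) = 2.96%
- Cumulative incidence = (0.01/0.11) × [1 − exp(−0.33)] = 0.0909 × 0.2811 = 2.56%
- First event = 28.1%
- Repair alone: 25.9% by one minus Kaplan-Meier, 25.6% by cumulative incidence

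With p = 0.01 and r varied:

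| Repair hazard per year | Rupture, 1 − KM | Rupture, cumulative incidence | Ratio |
|---|---|---|---|
| 0.02 | 2.96% | 2.87% | 1.03 |
| 0.05 | 2.96% | 2.75% | 1.08 |
| 0.10 | 2.96% | 2.56% | 1.16 |
| 0.20 | 2.96% | 2.23% | 1.33 |
| 0.30 | 2.96% | 1.95% | 1.51 |

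The ratio hardly changes with p. The absolute excess runs from 0.02 percentage points (r = 0.02, p = 0.002) to 2.0 (r = 0.30, p = 0.02: 5.82% against 3.86%).

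**3. How many ruptures.** Protocol 4.4 reports 32 patients enrolled of 114 planned when recruitment was reviewed. With r = 0.10 and p = 0.01, the expected number is 32 × 0.0256 = 0.8. Over p = 0.002 to 0.02 and r = 0.05 to 0.20 it is about 0.1 to 1.7. At p = 0.005 the chance of no rupture at all is about 64 to 70%, and both estimates are then zero.

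**4. The time axis pulls the other way.** Time runs from diagnosis, which may be up to 60 months before screening. At least two CT scans 20 or more weeks apart must follow diagnosis, and patients must be unrepaired and unruptured at entry (Protocol 5.1.1). No event can therefore be observed before entry, yet the SAP counts each patient as at risk from diagnosis. I simulated 400,000 patients with entry uniform between 20 weeks and 60 months after diagnosis, plus one month, and 3 years of follow-up. With r = 0.10 and p = 0.01, the SAP's rupture estimate is 0.03% at 12 months and 0.63% at 36 months from diagnosis. Cumulative incidence under the same hazards is 0.95% and 2.56%. In all five hazard pairs simulated, the SAP estimate was below cumulative incidence at every reporting time from 6 to 36 months. The entry distribution is an assumption too.

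**The case against.** The best defence is that the SAP does what Protocol 12.7 asks. The endpoints under objective 1 are dates, 12.7 lists two separate times, and neither document states a composite or a first-event rule. This stands in part. A reader might infer that the SAP dropped a stated endpoint, and the documents do not support that. The mismatch lies between the wording of the objective and the analysis text of both documents. It still leaves the repair-or-rupture time without an estimate.

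A reader might also infer that the plan overstates rupture risk. That does not follow either. The excess is relative to cumulative incidence on the same time axis, it is zero if no rupture follows a repair, and the missing late-entry adjustment can outweigh it. If repair selects patients at higher risk of rupture, the curve would also understate the risk in the absence of repair.

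Other planned outputs cover some of the ground. Protocol 12.7 plans patient counts for each event, and SAP 9.5.2.1.2 plans person-year rates from randomization and a patient listing. The rates do not share the Kaplan-Meier problem, but they give no time from diagnosis.

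Finally, the analysis is secondary and descriptive with no hypothesis test, and few ruptures are expected. That limits the severity. It does not make the separate curves the right display for this objective. An opposing bias from late entry is a second thing to correct, not a defence of the first.

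**Conclusion.** The point holds as a mismatch and a choice of estimator. Objective 1 reads as time to repair or rupture, while Protocol 12.7 and SAP 9.5.2.1.1 analyse the two only separately, with each terminal event treated as ordinary censoring in the other's curve.

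For rupture on a common axis, one minus Kaplan-Meier exceeds cumulative incidence by a factor of about 1.03 to 1.51 at 3 years, and by at most about 2 percentage points. This rests on assumed constant, independent hazards. For repair the gap is smaller: 25.9% against 25.6% in the worked case. The net direction of the SAP's rupture estimate on its own time axis is not established.

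Severity is modest. The change is worth making because it gives a stated objective an estimate that uses every event in a small trial. The gain in events over repair alone may be slight: under the worked assumptions 32 × 0.281 = 9.0 first events, against 32 × 0.256 = 8.2 repairs.

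**What to change.** - Reconcile objective 1 with Protocol 12.7 and the SAP by stating that it means time to the first of repair decision or rupture.
- Add a Kaplan-Meier analysis of that time, by arm, as the main display for objective 1. State how a repair decided on or after the day of rupture is classified, and how death is handled, since it remains a competing event for the combined time.
- Show repair and rupture separately as Aalen-Johansen cumulative incidence, with the other event and death as competing events, in place of the two planned curves.
- Keep time from diagnosis as the axis, but count patients as at risk only from study entry (left truncation). Show numbers at risk throughout, because few patients may be at risk soon after diagnosis and the first reporting times may not be estimable.

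The diagnosis, repair-decision and rupture dates are already collected. The cost is SAP wording, one more curve and table, and code changes to carry an entry time and a competing-event status. If the SAP is not reopened before database lock, SAP section 1 allows supplementary analyses to be described in the clinical study report.
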